10.2.3.6 Adverse Events

Adverse Event Definition

An AE is defined as any untoward medical occurrence in a clinical study patient administered a study medication and which does not necessarily have a causal relationship with this treatment. A TEAE is an AE with a start date on or after the initial dose of study medication and up to 5 days after the last dose of study medication. An AE can therefore be any unfavorable and unintended sign (including an abnormal laboratory finding), symptom, or disease temporally associated with the use of the study medication, whether or not related to the study medication. This includes an exacerbation of pre-existing conditions or events, intercurrent illnesses, drug interaction, or the significant worsening of the indication under investigation that is not recorded elsewhere in the eCRF. Anticipated fluctuations of pre-existing conditions, including the disease under study, that do not represent a clinically significant exacerbation or worsening need not be considered AEs. **Migraine headaches will not be captured as AEs.** Migraine headaches will be captured by the patient in the eDiary provided to them.

For the purpose of the site's data collection responsibilities, any untoward event that started or worsened after the informed consent form (ICF) was signed until the final end-of-study visit (inclusive) is to be considered an AE.

It is the responsibility of the Investigator to document all AEs that occur during the study. Adverse events will be elicited by asking the patient a non-leading question, for example, "Have you experienced any new or changed symptoms since we last asked/since your last visit?" Adverse events should be reported on the appropriate page of the eCRF.

CONFIDENTIAL

Assessment of Severity

Each AE will be assigned a category by the Investigator as follows:

Mild	An AE that is easily tolerated by the patient, causes minimal discomfort, and does not interfere with everyday activities.
Moderate	An AE that is sufficiently discomforting to interfere with normal everyday activities; intervention may be needed.
Severe	An AE that prevents normal everyday activities; treatment or other intervention usually needed.

If there is a change in severity of an AE, it must be recorded as a separate event.

Assessment of Causality

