- Description of the symptom event
- Classification of "serious" or "not serious"
- Severity
- Date of first occurrence and date of resolution (if applicable)
- Action taken
- Causal relationship
- Outcome of event (unknown, recovered, not yet recovered, recovered with sequelae, death [with date and cause reported]).

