11.6.6 Safety Analysis

All AEs will be coded using the latest version of the Medical Dictionary for Regulatory Activities (MedDRA) version 19.0 or higher. A TEAE is an AE with a start date on or after the initial dose of study medication and up to 5 days after the last dose of study medication. Only TEAEs will be included in summary tables. Migraine headaches will not be captured as AEs. Migraine headaches will be captured by the patient in the eDiary provided to them at screening. The information will then be entered into the appropriate eCRF page.

The incidence of all TEAEs will be tabulated by treatment received. These TEAEs will be classified by system organ class (SOC) and preferred term (PT). For incidence reporting, if a patient reported more than one AE that was coded to the same SOC or PT, the patient will be counted only once for that specific SOC or PT.

An overview of AEs, which includes patient incidence of TEAEs, headache or migraine-related TEAEs, study medication-related TEAEs, and SAEs, will be presented. The patient incidence of TEAEs, headache- or migraine-related TEAEs, study medication-related TEAEs, and SAEs will be summarized by SOC and PT.

CONFIDENTIAL

Treatment-emergent adverse events will also be summarized in a table by severity. For TEAEs presented by severity, the worst severity during the study will be presented for each patient, SOC, and PT.

Treatment-emergent adverse events will also be summarized in a table by relationship to study medication. For TEAEs presented by relationship to study medication, the strongest relationship to study medication during the study will be presented for each patient, SOC, and PT.

All AEs will also be presented in a by-patient data listing.

All prior and concomitant medications will be classified using the Anatomical Therapeutic Chemical (ATC) classification and preferred drug names from the World Health Organization Drug Dictionary (WHO-DD), version March 2016 or later. Medications will be considered concomitant if they were taken at any time between the date of first dose and the date of last dose of study medication, inclusive. Medications will be considered as prior if stopped before the date of first dose of study medication during the DB1 treatment period.

Prior and concomitant medications will be summarized in separate tables by ATC level 2 and preferred drug name for the safety population.

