6.2.5. Treatment Emergent Adverse Events

A TEAE for DB1 is defined as an AE that started on or after the first dose of study medication (DFN-02 or placebo) in DB1 or any existing AE that worsens in severity on or after the date of the first dose of study medication in DB1 up to 5 days after the date of the last dose of study medication in DB1 or up to taking DB2 study medication, whichever occurs first.

A TEAE for DB2 is defined as an AE that started on or after the first dose of study medication (DFN-02 or placebo) in DB2 or any existing AE that worsens in severity on or after the date of the first dose of study medication in DB2, up to 5 days after the date of the last dose of study medication in DB2.

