9.3. ADVERSE EVENTS

All AEs will be coded using the Medical Dictionary for Regulatory Activities (MedDRA; version 19.0 or higher). Migraine headaches will not be captured as AEs. Migraine headaches will be captured by the subject in the eDiary provided to them, and the information will be entered into the appropriate eCRF page.

All AEs will be listed by subject. The following listings of AEs will be provided:

- All AEs
- Study medication-related AEs
- Serious adverse events (SAEs)
- AEs leading to death
- Adverse events leading to study medication termination

Statistical Analysis Plan

Final V1.0

[name], Ltd.
Protocol #DFN-02-CD-012
INC Research #1007752

Only TEAEs will be included in summary tables. Summaries for AEs will be presented for the SS, SS1, and SS2. An overall summary table of TEAEs will be produced for the following categories:

- Any TEAE
- Study medication-related TEAEs
- Serious TEAEs
- TEAEs leading to study medication termination
- TEAEs leading to death

All TEAEs will be classified by system organ class (SOC) and preferred term (PT). Frequency count and the number of unique subjects of a TEAE will be tabulated by treatment(s) received. For the number of unique subjects reporting, if a subject reported more than one AE that was coded to the same SOC or PT, the subject will be counted only once for that specific SOC or PT.

The following summaries of TEAEs will also be provided:

- TEAEs by SOC and PT
- Study-medication related TEAEs by SOC and PT
- Serious TEAEs by SOC and PT
- TEAEs by maximum severity (mild, moderate, severe or missing) by SOC and PT
- TEAEs by strongest causality relationship (not related, possibly related, probably related, definitely related or missing) by SOC and PT

For TEAEs presented by relationship to study treatment(s), the strongest relationship to study treatment(s) during the study will be presented for each subject if coded to the same SOC or PT. For TEAEs presented by severity, the worst severity during the study will be presented for each subject if coded to the same SOC or PT. TEAEs with missing causality will be counted as related. TEAEs with missing severity will be counted as severe. The same will be true in the individual summaries.

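### Each change in AE severity becomes a separate record that the SAP never recombines, so the TEAE event count is inflated and, depending on the date entered, an easing AE can be counted as treatment-emergent

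*SAP*

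**What the plan says.** **Recording (Protocol 10.2.3.6).** The rule on severity is: "If there is a change in severity of an AE, it must be recorded as a separate event". It is mandatory and has no direction, so it covers improvement as well as worsening. Collection begins at consent and covers "any untoward event that started or worsened after the informed consent form (ICF) was signed until the final end-of-study visit (inclusive"), so AEs present before dosing are in the database. Among the items to be documented for each AE is "Date of first occurrence and date of resolution (if applicable").

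**TEAE definition.** Protocol 11.6.6 goes by start date alone: "A TEAE is an AE with a start date on or after the initial dose of study medication", with a limit of 5 days after the last dose. SAP 6.2.5 has two limbs for each period. The first is "A TEAE for DB1 is defined as an AE that started on or after the first dose of study medication". The second is "any existing AE that worsens in severity on or after the date of the first dose of study medication in DB1". The DB1 window runs "up to 5 days after the date of the last dose of study medication in DB1" or until DB2 medication is taken, whichever comes first. The DB2 definition has the same two limbs and the 5-day limit.

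**Counting (SAP 9.3).** "Frequency count and the number of unique subjects of a TEAE will be tabulated by treatment(s) received". A subject with several AEs under one SOC or PT is counted once in the subject count. The severity and relationship tables use the worst severity and the strongest relationship per subject. No such rule is given for the frequency count.

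**The concern.** The second limb of SAP 6.2.5 shows the intent: an AE already present at dosing should count only if it gets worse. That works if an AE is one record whose severity can be followed over time. The protocol's recording rule breaks an AE into one record per severity level instead. A record created because an AE eased can then satisfy the first limb by itself, and the worsening condition is never applied.

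The same splitting affects the event count. Without a rule to rejoin the records, the frequency column reflects how often an AE changed severity as well as how many AEs occurred.

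Tolerability by AEs is a stated objective and safety endpoint for each period and overall, and subjects are re-randomized for DB2. An AE from DB1 that eases after the DB2 dose could therefore appear as a DB2 TEAE under a different treatment from the one taken when it arose.

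**Working it through.** The plan gives no figure to reproduce. The check applies the recording rule (Protocol 10.2.3.6), the TEAE rule (SAP 6.2.5) and the counting rule (SAP 9.3) in turn to three illustrative AE histories. These histories are assumptions, not trial data, and all records are taken to fall within the relevant window. Because the documents do not say which start date the separate record carries, both conventions are shown.

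| AE history | Evident intent of SAP 6.2.5 | New record dated from the change | New record keeps the original onset |
|---|---|---|---|
| A. Moderate before the dose, mild after it | 0 events, 0 subjects | 1 event, 1 subject | 0 events, 0 subjects |
| B. Starts after the dose: mild, moderate, mild | 1 event, 1 subject | 3 events, 1 subject | 3 events, 1 subject |
| C. Starts after the DB1 dose, eases after the DB2 dose | DB1: 1 event; DB2: 0 | DB1: 1 event; DB2: 1 event, 1 subject | DB1: 2 events, 1 subject; DB2: 0 |

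**Part (a), the event count.** An AE with k severity changes has k + 1 records. In history B, k = 2, so the frequency count is 2 + 1 = 3 where one AE occurred. This holds under either date convention, because every record starts after the dose. The unique-subject count stays at 1, and the maximum-severity and strongest-relationship tables also take the subject once per SOC or PT.

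**Part (b), the easing AE.** In history A the second limb fails, since severity went down. The first limb is met only if the mild record has a start date after the dose. History C behaves the same way in DB2, and the record is tabulated under the re-randomized treatment.

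**Which date is likelier?** The protocol's TEAE definition has no worsening limb. Under it, an AE that began before dosing and then worsened can be treatment-emergent only if its separate record starts at the change. That favours dating from the change. Against it, the documented item refers to the first occurrence, which can be read as the original onset. The point remains open.

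**Size of (b).** SAP 3.6 plans 50 subjects per DB1 arm. One additional subject in a row moves its incidence by 1/50 = 2 percentage points. This is a ceiling per subject: the increment is 0 if the subject already has a TEAE in that row, and a second such AE in the same subject adds nothing to the same row. For an arm of n dosed subjects the step is 1/n, so it is larger where fewer than 50 are treated.

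**The case against.** The strongest reply is that the recording rule calls for a separate event but says nothing about its start date. If sites enter the original onset, an easing predose AE has a predose start and the first limb does not catch it. This stands, and part (b) is therefore conditional. It does not affect part (a).

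A second reply is that the two limbs should be read together: if every severity record were a new AE, the worsening limb would be redundant, so improvement is excluded by implication. Site collection is also framed around events that started or worsened, and Protocol 10.2.3.6 exempts expected fluctuation of pre-existing conditions. This is good evidence of intent. But the exemption concerns pre-existing conditions, not AEs already on the form, and intent does not tell a programmer what to do with a mild record dated after the dose.

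Third, no linking field in the documented AE items does not prove that the eCRF lacks one, since the eCRF specification is not among the documents. AEs are listed by subject and Protocol 11.1 provides for a blinded data review, so split records could be noticed. Both points stand, but neither supplies a derivation rule.

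A reader might infer more than the documents support: that every AE that eases after dosing becomes a TEAE, that fluctuating AEs inflate all the AE tables, or that the comparison is biased against one treatment. The first depends on the date convention and the window. The second is contradicted by the once-per-subject rule in SAP 9.3. For the third, AEs present before a period's dose are expected to be balanced by the blinded randomization, so no direction of bias is shown. AE tables are descriptive; hypothesis testing is planned for efficacy only.

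**Conclusion.** The point holds in two parts of different strength.

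(a) Followed as written, the rules make the TEAE event frequency count one fluctuating AE once for each severity record that qualifies. This needs no assumption about the date entered when the AE starts after dosing and its records fall within the window. It is confined to the event count.

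(b) If the separate record starts on the date of the severity change, which is likely but not stated, an AE that was present before dosing or carried over from DB1 and eases within the window is tabulated as a TEAE. This reaches the subject counts, by at most about 2 percentage points per affected subject in a 50-subject arm.

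How often either occurs cannot be derived from the documents, and the number of affected records may be small. It is still more than a missing detail: rules that are stated combine to give a wrong event count and possibly a wrong subject count, and two programmers following the SAP could produce different TEAE tables. The efficacy analyses are not affected.

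**What to change.** **SAP 6.2.5.** Before applying the TEAE rule, link contiguous records of the same preferred term within a subject into one AE. Use recorded dates for this. SAP 6.3 imputes partial AE start dates to the period's dose date or to the start of the month or year, which can create or destroy contiguity, so records with partial or imputed dates should be resolved by blinded review before unblinding. Then call the linked AE a TEAE for a period only if

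- its first record starts at or after that period's first dose, within the window; or
- a later record within the window is more severe than the last record before that dose.

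A fall in severity then never makes an AE treatment-emergent, whichever date convention the sites used.

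**SAP 9.3.** Count each linked AE once in the frequency count, at its maximum severity within the period. The unique-subject rules can stay as they are.

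**Effect on the illustrations.** History A gives 0 events and 0 subjects; B gives 1 event and 1 subject; C gives 1 event in DB1 and none in DB2.

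**Cost.** A few sentences in the SAP, a short derivation step and a blinded check of the few affected records. No new data collection is needed.

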6.3. MISSING DATA

Subjects are allowed to withdraw from the study at any time. Subjects who withdraw from the study will have all data listed and, wherever relevant, included in any subject summaries. Analyses on quantitative and categorical variables will include data from subjects with non-missing values. Partial dates will be listed as recorded on the case report form (CRF). Imputation of missing or incomplete dates will only be performed for summaries of AEs and concomitant medications unless otherwise specified.

Partial Missing Start or Stop Date	Imputed Start Date	Imputed Stop Date
Missing month and day, and the year is present	January 1 of that year or DB period dose date if the	December 31 of that year

Statistical Analysis Plan

Final V1.0

[name], Ltd.
Protocol #DFN-02-CD-012
INC Research #1007752

Partial Missing Start or Stop Date	Imputed Start Date	Imputed Stop Date
	year is the same as the year of the DB period dose date	
Missing day, but year and month are present	First day of that month or DB period dose date if the year and month are the same as the year and month of the DB period dose date	Last day of that month
Missing month, but year and day are present	Missing month imputed as January	Missing month imputed as December

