7.5.2. Prior and Concomitant Medications

All prior and concomitant medications will be classified using the Anatomical Therapeutic Chemical (ATC) classification and preferred drug names from the World Health Organization Drug Dictionary (WHO-DD), version March 2016.

Summaries of medications will be presented in tabular form using the highest level ATC term as an upper classification and the preferred drug name as a lower classification level. All medications will be summarized by dose level and sorted by descending counts in the upper classification term and the lower classification term within the upper. The summary will consist of the frequency and percentage of subjects who used the medication at least once. For each subject, the medication will be counted only once within the upper classification level and only once within the lower classification level.

Medications will be considered prior if stopped before the DB1 dose date. Medications with a start or stop date on or after the DB treatment period dosing date will be considered concomitant medications. If a concomitant medication starts on or after the start time of DB1 dose administration, it is considered a concomitant medication to the study treatment in DB1, but not in DB2. If a concomitant medication starts on or after the start time of DB2 dose administration, it is considered a concomitant medication to the study treatment in DB2. All medications marked as ongoing are concomitant medications. A medication with an incomplete start/stop date will have its date imputed as described in SAP Section 6.3 solely to determine if the medication is prior or concomitant.

Summaries of prior and of concomitant medications will be presented separately in tables and will be based on the SS. Prior and concomitant medications will be listed by subject. An identifier will be included to show if a medication is prior or if it is concomitant with respect to the applicable DB treatment period.

Statistical Analysis Plan
Final V1.0

[name], Ltd.
Protocol #DFN-02-CD-012
INC Research #1007752

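### SAP 6.3 moves a partial start date to the dose date without checking a known stop date, so an AE that ended before dosing becomes a TEAE and a drug stopped before the DB1 dose becomes both prior and concomitant

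*SAP*

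**What the plan says.** SAP 6.3 limits date imputation to two uses: "Imputation of missing or incomplete dates will only be performed for summaries of AEs and concomitant medications unless otherwise specified". Its table has three rows for start dates:

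- Month and day missing: "January 1 of that year or DB period dose date if the" year is also the year of the dose.
- Day missing: "First day of that month or DB period dose date if the year and month are the same as the year and month" of the dose.
- Month missing but day known: "Missing month imputed as January".

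The first two rows can return the dose date. None of the three refers to the stop date.

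Three classification rules then use the imputed start:

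- SAP 6.2.5, DB1: "A TEAE for DB1 is defined as an AE that started on or after the first dose of study medication", with a parallel rule for the second period: "A TEAE for DB2 is defined as an AE that started on or after the first dose of study medication". Worsening of an existing AE also counts. Each window closes 5 days after the last dose of its period, and the DB1 window closes earlier if DB2 medication is taken.
- SAP 7.5.2, prior: "Medications will be considered prior if stopped before the DB1 dose date".
- SAP 7.5.2, concomitant: "Medications with a start or stop date on or after the DB treatment period dosing date will be considered concomitant medications".

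SAP 7.5.2 uses the dates imputed under 6.3 to decide between prior and concomitant. SAP 9.3 restricts the AE summary tables to TEAEs.

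**The concern.** Moving an incomplete start to the dose date is a sensible cautious default when nothing shows that the event came earlier. Here the default also applies when the stop date proves that it did. The result is a record that starts after it ends and is then classified on that impossible start.

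Records that end before dosing will exist. AEs are collected from informed consent (Protocol 10.2.3.6), and prior medications are recorded back to at least 1 year before screening (Protocol 9.5).

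For AEs, an event that belongs only in the listings is charged to a randomized arm. For drugs, one record goes into both the prior and the concomitant table. The second placement also conflicts with Protocol 11.6.6, which calls a drug concomitant only if it was taken between first and last dose. SAP 11 does not list this as a change.

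One visible consequence is possible. Patients keep their usual migraine medication during screening (Protocol 6.1), while triptans other than study medication are prohibited (Protocol 9.5.3). A screening triptan with a year-only start in the dosing year and a known stop before dosing would be tabulated as concomitant, and would look like prohibited use.

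**Working it through.** The plan gives no figure on this point to reproduce. The check applies the rules as written to hypothetical records, then repeats it with a stop-date condition.

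**Inputs.** Start-date rows: SAP 6.3. TEAE rule: SAP 6.2.5. Prior and concomitant rules: SAP 7.5.2. Assumed DB1 dose: 20SEP2016.

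| Recorded start | Recorded stop | Start under 6.3 | As an AE | As a drug | With a stop-date check |
|---|---|---|---|---|---|
| SEP2016 | 10SEP2016 | 20SEP2016, 10 days after the stop | DB1 TEAE | prior and concomitant | 01SEP2016: no TEAE, prior only |
| 2016 | 15MAR2016 | 20SEP2016 | DB1 TEAE | prior and concomitant | 01JAN2016: no TEAE, prior only |
| AUG2016 | 10SEP2016 | 01AUG2016 | no TEAE | prior only | unchanged |
| day 5, month missing, 2016 | 10SEP2016 | 05JAN2016 | no TEAE | prior only | unchanged |

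The second row is realistic only for a drug, since an AE that ended in March would normally precede consent. The last two rows show the limits of the problem: a partial start in an earlier month, or with only the month missing, is not moved to the dose date.

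**How often an eligible record is misclassified.** Assume a 49-day pre-dose window (21 days of screening plus 28 days to treat, from Protocol 10.1) and equal weight for every start and stop pair with start ≤ stop < dose.

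- All pairs: 49 × 50 / 2 = 1225.
- Day missing, dose on day *d* of the month: the start must lie in the *d* − 1 earlier days of that month, which gives (*d* − 1) × *d* / 2 pairs.
 - *d* = 5: 4 × 5 / 2 = 10, or 0.8%.
 - *d* = 15: 14 × 15 / 2 = 105, or 8.6%.
 - *d* = 20: 19 × 20 / 2 = 190, or 15.5%.
 - *d* = 31: 30 × 31 / 2 = 465, or 38.0%.
- Month and day missing, all dates in the dosing year: 1225 of 1225, or 100%.
- With the stop-date check (run for doses on 5 and 20 September and 15 December 2016): 0 of 1225 in each case.

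These shares are conditional on a record that already has a partial start and a known pre-dose stop. They are not rates for the trial.

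**Weight of one record.** SAP 3.6 plans 50 subjects per DB1 arm, so one wrongly counted subject is 1 / 50 = 2 percentage points.

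**Two dose dates.** A subject who continues has a DB1 and a DB2 dose within a span of up to 10 weeks, so both often fall in one year and can fall in one month. SAP 6.3 refers only to the DB period dose date and does not say which is meant. A record that ended between the two doses can likewise be moved to the DB2 dose date, after its own stop.

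**The case against.** The strongest case on the other side has five parts.

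1. **Few records qualify.** The protocol requires the date of first occurrence and of resolution for each AE (10.2.3.6), AEs are reviewed at every visit, and missing or inconsistent data are queried (12.1.3). A year-only AE start in a study of about 13 weeks is remote. This stands as a limit on size. It does not supply a rule for the partial dates that remain.
2. **The rule is the same in both arms and tends to over-count.** No mechanism for bias between arms is shown, and the primary endpoint is untouched. This stands. Caution still does not justify a start later than a known stop.
3. **For drugs, the prior rule may settle the matter.** A complete stop before the DB1 dose already makes a drug prior, and the listing identifier treats the classes as alternatives. That may be the intent. But the concomitant definition is met by a start or a stop on or after dosing, the imputed start meets it, and no order of precedence is given.
4. **A reader might infer that one AE is counted in both periods, and so charged to two treatments.** That would follow if each period were imputed separately, which the SAP does not say. SAP 6.2.5 closes the DB1 window at DB2 dosing, and SAP 7.5.2 assigns a drug started on or after the DB1 dose to DB1 and not DB2. Both lean towards one period per record. The text supports an ambiguity, not proven double counting.
5. **A reader might expect many affected drugs, because Protocol 9.5 collects neurological medications taken at any time in the past.** Most would not be affected: a partial start in a year before the dosing year goes to 1 January or the first of the month, never to the dose date.

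**Conclusion.** The concern holds for the two rows that can return the dose date. As written, they can give an AE or a drug a start later than its known stop, and the definitions in SAP 6.2.5 and 7.5.2 then classify it wrongly. Nothing elsewhere in the protocol or SAP corrects this. It is a stated rule with a wrong result, not just missing detail.

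The misclassification is limited to records with a partial start in the dosing month or year and a known stop before the dose. The documents do not allow their number to be estimated. The percentages above rest on an assumed 49-day window and equal weights, and show only how the rule behaves once such a record exists. The effect is confined to descriptive safety and medication tables, where one subject is 2 percentage points of an arm. No efficacy result depends on it. The choice between two matching dose dates is a separate gap that should be closed by a statement. The change is worth making because it is nearly free and removes impossible records.

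**What to change.** Make three changes before unblinding.

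- **SAP 6.3, first two rows, add:** *Impute the dose date only if the stop date is missing, ongoing, or on or after that dose date; otherwise use the first day of the known month or year. An imputed start may never be later than a known stop date.*
- **SAP 7.5.2, add:** *A medication with a known stop before the DB1 dose is prior only.*
- **SAP 6.3, state** which DB dose date is used when both fall in the known month or year, and that a single AE record imputed this way is assigned to one period only. The documents do not favour either date, so the sponsor should choose and record the choice.

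The cautious default stays in place wherever the stop date leaves the start open. The cost is a few sentences in the SAP or in a note to file, plus one condition in the date derivation program. No new data are needed.

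### SAP 6.3 dates an AE with only the start month missing to January, so a true treatment-emergent AE with onset outside January can drop out of the TEAE tables

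*SAP*

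**What the plan says.** SAP 6.3 limits date imputation, unless otherwise specified, to the summaries of AEs and concomitant medications. It covers three patterns of partial start date:

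- Month and day missing: "January 1 of that year or DB period dose date if the" "year is the same as the year of the DB period dose date" (the cell runs over a page break).
- Day missing: "First day of that month or DB period dose date if the year and month are the same" as those of the dose.
- "Missing month, but year and day are present": "Missing month imputed as January". This cell does not mention the dose date.

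SAP 6.2.5 makes treatment emergence depend on onset: "A TEAE for DB1 is defined as an AE that started on or after the first dose of study medication". Existing AEs that worsen also count. The window closes 5 days after the last dose of the period, or at the DB2 dose if that comes sooner for DB1. DB2 has a matching definition.

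SAP 9.3 adds: "Only TEAEs will be included in summary tables". It also provides by-subject listings of all AEs, and SAP 6.3 lists partial dates as recorded. Neither SAP 11 nor the two notes to file alters the missing-month row.

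**The concern.** Two of the three rows protect against losing a post-dose event, and the third does not. As a result, more information gives a worse classification: an AE known only by year can be moved to the dose date and counted, while the same AE with its day also recorded is moved to January and excluded.

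This also runs against the SAP's own treatment of incomplete AE data. SAP 9.3 counts missing causality as related and missing severity as severe.

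Tolerability assessed by AEs is a stated secondary objective and a safety endpoint, and the groups are small (about 50 per arm), so a single subject shows in an incidence table.

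**Working it through.** The plan gives no figure to reproduce here. The check applies the three rows to known onsets and sees which remain TEAEs.

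**Inputs**

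- Imputation rows: SAP 6.3.
- TEAE window: SAP 6.2.5. For a single dose it runs from the dose date to dose date + 5 days, which is 6 calendar days.
- Earliest calendar date: 1 June 2016, the protocol date (also cited in SAP 11).
- Latest calendar date: 23 March 2017, the date of the last note to file.
- Dosing dates: not in the documents, so every calendar below is an assumption.

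**One example (assumed dates).** Dose 12 October 2016, true onset 14 October 2016, month not recorded.

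- Missing-month row: 14 January 2016. This is 272 days before the dose, so the AE is not a TEAE. It is also before the protocol was dated, and so before any consent, although AEs are reported only from consent (Protocol 10.2.3.6).
- If the day were also unknown: the year matches the dose year, so the date becomes 12 October 2016 and the AE is a TEAE.

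**Enumeration.** Each dose date in the range is paired with each true onset from day 0 to day 5. Number of cases = number of dose dates × 6. A case is kept if dose ≤ imputed start ≤ dose + 5.

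| Assumed dosing range | Cases | Kept, missing-month row | Kept, other two rows |
|---|---|---|---|
| 1 Jun to 26 Dec 2016 | 209 × 6 = 1254 | 0 (0%) | 100% |
| 1 Jun to 31 Dec 2016 | 214 × 6 = 1284 | 15 (1.2%) | 100% |
| 1 Jun 2016 to 23 Mar 2017 | 296 × 6 = 1776 | 186 (10.5%) | 100% |
| 1 to 26 Jan 2017 | 26 × 6 = 156 | 156 (100%) | 100% |
| 1 Feb to 23 Mar 2017 | 51 × 6 = 306 | 0 (0%) | 100% |

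The missing-month row keeps a case only when the true onset is in January. The table covers true TEAEs only. It measures sensitivity and says nothing about false positives.

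**Does another rule recover the event?** The December imputation for stop dates does not, because emergence depends on onset. Nor does the worsening clause: Protocol 10.2.3.6 records a change in severity as a separate event, which has its own start date.

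**Size of one loss.** 1/50 = 2 percentage points of TEAE incidence in an arm of 50 (Protocol 11.8).

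**The case against.** Three stronger readings are tempting, and the documents do not support them.

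- *Every AE with this pattern is misclassified.* AEs are collected from consent, so they include roughly 3 weeks of screening and up to 4 weeks between randomization and dosing. Those AEs, and AEs starting more than 5 days after the last dose, are correctly non-emergent, and a pre-dose January date leaves them so.
- *The rule always under-counts.* It is right for January onsets, and it can over-count. With an assumed DB1 dose on 5 January 2017 and a true onset on 8 February 2017, it gives 8 January. That is a false TEAE or, if DB2 was dosed just before 8 February, an event assigned to the wrong period.
- *The event disappears.* It remains in the by-subject listings with its partial date, and in the separate listings of serious, related, fatal and treatment-ending AEs where it qualifies.

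The pattern should also be rare. V3 and V4 are expected 2 to 7 days after treatment, with AE review at each. Date of first occurrence is a required item (Protocol 10.2.3.6), missing data are queried (12.1.3), and a blinded review checks completeness (11.1). A site that knows the day and year of a recent AE would normally be able to supply the month.

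Finally, copying the dose-date fallback into this row would create a new error, because the recorded day carries information. For a single dose on 12 October the DB1 window is 12 to 17 October. A recorded day of 20 cannot fall in it in any month, yet the fallback would make the AE a TEAE and overwrite the recorded day. In a 31-day month, 31 − 6 = 25 days lie outside a single-dose window.

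All of this stands. It limits the size of the problem and shapes the fix, but it does not supply the missing comparison with the dose date.

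**Conclusion.** The point holds as a minor defect in one table cell. A true treatment-emergent AE with day and year recorded, month missing and onset outside January is dated before the dose of its period and is normally dropped from the SS, SS1 and SS2 TEAE tables. For 2016 onsets the imputed date also precedes any possible consent.

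The 0% to 10.5% retained applies to true TEAEs with this pattern, under assumed dosing calendars that start on 1 June 2016. Dosing confined to 1 to 26 January would give 100%. The number of such AEs cannot be estimated from the documents and may well be zero; each one affects an arm of 50 by about 2 percentage points. The efficacy analyses are untouched.

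**What to change.** Replace the start-date cell of the missing-month row, for AEs, with the following:

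1. Keep the recorded day and year. Consider only months that place the date between consent and the final visit and that agree with any known stop date.
2. If one of those months puts the recorded day inside the DB1 or DB2 TEAE window (first dose to 5 days after the last dose of that period, with DB1 ending at the DB2 dose if sooner), use that month and assign the AE to that period. If both periods qualify, use the earlier.
3. Otherwise use the earliest month on or after consent. The AE is then not treatment-emergent.
4. Use January only if the recorded year precedes the year of consent.

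In the October example, recorded day 14 becomes 14 October and is a TEAE. Recorded day 20 cannot be a DB1 TEAE. Every true TEAE is kept as a TEAE, because its true month is always one of the candidates.

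The cost is one SAP cell and a short piece of programming, set without reference to treatment assignment. The downside is that an AE which was not treatment-emergent may occasionally be counted, for example a screening AE whose day of the month happens to match the window. An event that fits both periods may also be assigned to the wrong one. The same row governs concomitant-medication start dates (SAP 7.5.2), so the new cell should state that it applies to AEs.
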